Complete safety tables will be provided for the Safety_A1 Population and the Safety_B_R population. Only AE overview tables will be provided for other safety populations.

The Safety Population will be analyzed based on the actual treatment received at the randomization visit (Part A) and at the re-randomization visit (Part B).

In addition, an All Risankizumab Treated Population (ALL_RZB) is defined as all subjects who receive at least one dose of risankizumab in the study. The ALL_RZB Population will be used for safety analyses. Complete safety tables will be provided in the ALL_RZB Population.

Table 1. Notations for Treatment Groups

Population	Treatment Code	Definition
ITT_A1/PP_A1/ Safety_A1	RZB	Subjects who randomized to risankizumab 150 mg.
	PBO	Subjects who randomized to placebo.
ITT_A2/Safety_A2	RZB/RZB	Subjects who randomized to risankizumab 150 mg.
ITT_ARM2/ Safety_ARM2	PBO/RZB	Subjects who randomized to placebo and received at least one dose of study drug on or after Week 16.
ITT_B_R/PP_B_R/ Safety_B_R	RZB/RZB/RZB	Subjects who re-randomized to risankizumab 150 mg at Week 28.
	RZB/RZB/PBO	Subjects who re-randomized to placebo at Week 28.
ITT_B_NR/Safety_B_NR	RZB/RZB/RZB	Subjects who randomized to risankizumab and are non-responders at Week 28.
ITT_B_PBO_RT/ Safety_B_PBO_RT	RZB/RZB/PBO/RZB	Subjects who received open-label risankizumab 150 mg as retreatment, after re-randomized to placebo in Part B.
ITT_B_RZB_RT/ Safety_B_RZB_RT	RZB/RZB/RZB/RZB	Subjects who received open-label risankizumab 150 mg as retreatment, after re-randomized to risankizumab in Part B.
ALL_RZB	RZB	Subjects who received at least one dose of risankizumab 150 mg.

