9.0 Study Drug Exposure and Compliance

Summary of study drug exposure will be provided for each treatment arm for all ITT_A1, ITT_A2, ITT_ARM2, ITT_B_R, and ITT_B_NR populations, and the ALL_RZB population. Study drug compliance will be summarized in ITT_A1, ITT_A2, and ITT_B_R populations.

Study drug exposure (days) will be summarized using the sample size, mean, standard deviation, minimum, median and maximum for each treatment part. In addition cumulative exposure of RZB will be also summarized in the ALL_RZB Population. Study drug exposure will be summarized as follows:

Study Drug Exposure (in Days) in Each Period:

Part A1:

For subjects who did not continue into Part A2:

- Date of last injection in Part A1 – Date of first injection in Part A1 + 84.

For subjects who continued into Part A2: the minimum of

- Date of first injection in Part A2 – Date of first injection in Part A1.
- Date of last injection in Part A1 – Date of first injection in Part A1 + 84 days.

Part A2:

For subjects who did not continue into Part B:

- Date of last injection in Part A2 – Date of first injection in Part A2 + 84 days.

For subjects who continued into Part B: the minimum of

- Date of first injection in Part B – Date of first injection in Part A2.
- Date of last injection in Part A2 – Date of first injection in Part A2 + 84 days.

Part B:

For subjects who did not receive retreatment with risankizumab: the minimum of

- Date of last injection in Part B – Date of first injection in Part B + 84 days.
- Cutoff date of 01 September 2017 – Date of first injection in Part B (only for the primary analysis after the last patient either has completed Week 52 visit or discontinues from the study)

For subjects who received retreatment with risankizumab: the minimum of

- Date of first injection of retreatment – Date of first injection in Part B.
- Date of last injection in Part B – Date of first injection in Part B + 84 days.
- Cutoff date (01 September 2017) – Date of first injection in Part B (only for the primary analysis after the last patient either has completed Week 52 visit or discontinues from the study)

ALL_RZB:

For subjects who were re-randomized to placebo in Part B and received retreatment with risankizumab: the minimum of

- Date of last injection of risankizumab in Part A – Date of first injection of risankizumab + 84 days + Date of last retreatment of risankizumab – Date of first retreatment of risankizumab + 84 days.

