For subjects who do not receive retreatment with risankizumab, TEAEs are defined as any event with an onset after the first dose of study drug in Part B and no more than 105 days after the last dose of study drug in Part B.

For subjects who receive retreatment with risankizumab, TEAEs are defined as any event with an onset after the first dose of study drug in Part B and before the first dose of retreatment with risankizumab.

TEAEs of Safety_B_PBO_RT and Safety_B_RZB_RT:

TEAEs are defined as any event with an onset that is after the first dose of retreatment and no more than 105 days after the last dose of study drug.

TEAE of ALL_RZB:

TEAEs are defined as any event with an onset after the first dose of risankizumab through 105 days after the last dose of risankizumab, except for AEs with an onset during protocol-designed treatment gaps (i.e., placebo period) that was more than 105 days from the last dose of the previous risankizumab treatment and before the first dose of retreatment.

Summary tables will be presented as follows:

1. Adverse Event Overview

The number and percentage of subjects experiencing treatment-emergent adverse events will be summarized for the following adverse event categories:

- Any AE
- Any AE that was assessed as related to study drug by the investigator
- Any severe AE
- Any serious AE (SAE)
- Any serious AE that was assessed as related to study drug by the investigator
- Any AE leading to discontinuation of study drug
- Any AE leading to death
- Any deaths
- Areas of Safety Interest

2. Adverse Events by System Organ Class and Preferred Term

TEAEs will be summarized and presented using primary Medical Dictionary for Regulatory Activities (MedDRA) system organ classes (SOCs) and preferred terms (PTs). The SOCs will be presented in alphabetical order, and the PTs will be presented in alphabetical order within each SOC.

Subjects reporting more than one adverse event for a given MedDRA preferred term will be counted only once for that term (most severe incident for the severity tables and most related incident for the relationship tables). Subjects reporting

more than one type of adverse event within a SOC will be counted only once for that SOC. Subjects reporting more than one type of adverse event will be counted only once in the overall total.

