ASI Grouping	Categories (ASI)	Search Criteria	Terms to Display	Include in AE Overview (Y/N)
Serious infections, TB, fungal and opportunistic infections (including herpes zoster) (continued)	Fungal infections	Fungal infections CMQ (code 80000063)	PTs	N
	Herpes Zoster	Herpes zoster CMQ (code 80000175)	PTs	N
Malignancies	All possible malignancies	Narrow – Malignancies (SMQ 20000090)	PTs	N
	Malignant Tumours	Narrow – Malignant tumours (SMQ 20000194)	PTs	Y
	Non-melanoma skin cancer (NMSC)	Broad – Skin malignant tumours (SMQ 20000204) excluding terms identified by the Melanoma CMQ (code 80000119)	PTs	N
	Malignant Tumours excluding NMSC	'Malignant Tumours excluding NMSC' is identified by the 'Malignant Tumours' search excluding terms identified by the 'Non-melanoma skin cancer (NMSC)' search.	PTs	Y

Table 23. Areas of Safety Interest (Continued)

ASI Grouping	Categories (ASI)	Search Criteria	Terms to Display	Include in AE Overview (Y/N)
Hypersensitivity Reaction	Hypersensitivity	Narrow – Hypersensitivity (SMQ 20000214)	PTs	Y – serious events only
	Anaphylactic Reaction	Narrow – Anaphylactic reaction (SMQ 20000021)	PTs	N
Hepatic Events	Hepatic Events	Broad – Hepatic failure, fibrosis and cirrhosis and other liver damage-related conditions (SMQ 20000013) Broad – Hepatitis, non-infectious (SMQ 20000010) Broad – Cholestasis and jaundice of hepatic origin (SMQ 20000009) Broad – Liver related investigations, signs and symptoms (SMQ 20000008) Narrow – Liver-related coagulation and bleeding disturbances (SMQ 20000015)	PTs	N

Adverse Event per 100 Patient-Years of Exposure

Adverse events occurring during the entire study will be presented by event rate per 100 patient-years. These will be presented for any TEAEs, serious adverse events, and Areas of Special Interest.

AEs per 100 patient-years of exposure is defined as the number of AEs divided by the total exposure in 100 patient-years. Note that one event per preferred term per day per subject will be counted in the calculation of the number of AEs (i.e., a preferred term will not be counted twice on the same day for the same subject). See the calculation method below.

$$100 \times \frac{\text{Number of TEAEs}}{\text{Total Patient Years}}$$

where total patient years is defined as the sum of the study drug exposure (defined as date of last dose – date of first dose + 105 days (5 half-lives)) of all subjects normalized by 365.25, and rounded to one decimal place.

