11.3 Analysis of Laboratory Data

For the assessments of laboratory data, values observed more than 105 days after the last dose of study drug will be excluded.

Listing and descriptive statistics of laboratory values over time, changes from baseline, and extreme abnormal value on treatment will be provided. Extreme abnormal value is the value which is most significantly away from the reference range. Frequency of subjects with transitions relative to reference range and listing of subjects with significant abnormal laboratory values will be presented as well.

Analyses will be conducted in the Safety_A1 Population, the Safety_B_R Population, and the ALL_RZB Population.

For subjects who were re-randomized to placebo in Part B, laboratory values evaluated after 105 days from the last dose of risankizumab in Part A and before the first dose of retreatment will not be included in the summaries for the ALL_RZB Population.

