11.4 Analysis of Vital Signs and Weight

Analyses will be conducted in the Safety_A1 Population, the Safety_B_R Population, and the ALL_RZB Population.

For subjects who were re-randomized to placebo in Part B, vital sign values evaluated after 105 days from the last dose of risankizumab in Part A and before the first dose of retreatment will not be included in the summaries for the ALL_RZB Population.

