11.5 Analysis of ECG Parameters

The ECG parameters will be assessed as scheduled in the study protocol.

Summary statistics for mean change from baseline for corrected QT interval (QTc) using Bazett (QTcB) and Fridericia (QTcF) corrections, aggregated, will be provided by analysis visits.

- Values for both QTcF and QTcB interval measurements will be categorized into the following: ≤ 450 ms, > 450 ms, > 480 ms, > 500 ms, or missing. For the scheduled visits, as well as baseline, the number and percentage of subjects within each category will be presented. Additionally, for each category, the number and percentage of subjects with a maximum QTcF interval falling into the category will be presented; a similar summary will be presented for QTcB intervals.
- For QTcF and QTcB intervals, the changes from baseline will be categorized into the following: < 30 ms, $30 \leq - < 60$ ms, ≥ 60 ms, or missing. For the scheduled visits, the number and percentage of subjects within each category will be presented. Additionally, for each category, the number and percentage of subjects with a maximum change from baseline in the QTcF interval falling into the category will be presented; a similar summary will be presented for QTcB intervals.

Analyses will be conducted in the Safety_A1 Population, the Safety_B_R Population, and the ALL_RZB Population.

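### If the AE rate per 100 patient-years is produced for ALL_RZB, its denominator keeps the placebo gap that the TEAE rule removes from the numerator, so the rate is too low

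*SAP*

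**What the plan says.** The rate is introduced in SAP 11.2.1 under Adverse Event per 100 Patient-Years of Exposure: "Adverse events occurring during the entire study will be presented by event rate per 100 patient-years". It covers any TEAE, serious AEs and the areas of interest. The denominator sums study drug exposure over patients, "defined as date of last dose – date of first dose + 105 days (5 half-lives". No population is named there, and SAP 17.0 leaves the list of tables to a separate document.

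SAP 5.1 defines ALL_RZB as everyone given at least one risankizumab dose, and adds: "Complete safety tables will be provided in the ALL_RZB Population". The ALL_RZB TEAE rule in 11.2.1 counts events from the first risankizumab dose to 105 days after the last, "except for AEs with an onset during protocol-designed treatment gaps (i.e., placebo period) that was more than 105 days from the last dose". Here the dose meant is the final risankizumab dose before withdrawal, and the gap ends when retreatment starts.

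Three other ALL_RZB rules also leave the gap out:
- SAP 9.0 adds a Part A span and a retreatment span for patients re-randomised to placebo and then retreated ("Date of first injection of risankizumab + 84 days + Date of last retreatment of risankizumab", and so on), each with an 84-day tail.
- SAP 11.3 excludes "laboratory values evaluated after 105 days from the last dose of risankizumab in Part A and before the first dose of retreatment".
- SAP 11.4 excludes "vital sign values evaluated after 105 days from the last dose of risankizumab in Part A and before the first dose of retreatment".

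ECG (11.5: "Analyses will be conducted in the Safety_A1 Population, the Safety_B_R Population, and the ALL_RZB Population") and local tolerability (11.6) state no gap rule.

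**The concern.** A patient withdrawn at Week 28 had the last risankizumab dose at Week 16, so the ALL_RZB event window closes at Week 31 and reopens only at retreatment. A single first-to-last-dose span still counts the weeks between. The numerator cannot grow in that time while the denominator does, so the error has one direction: a lower risankizumab rate.

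The meaning of dose is also open. The rate formula speaks of study drug, while the ALL_RZB event rule speaks of risankizumab. If placebo injections count as doses, withdrawn patients who never relapse add uncounted time as well.

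This is the only exposure-adjusted AE figure the SAP describes. Unequal follow-up is the reason for such a figure, and in this trial withdrawal with retreatment is a main source of it.

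**Working it through.** **Inputs**
- SAP 4.2: every patient gets one risankizumab dose at Week 16, and Arm 1 responders are re-randomised 1:2 at Week 28. Retreatment doses are at 0, 4 and 16 weeks (relapse Week 32 through 70), at 0 and 4 weeks (after Week 70 through 82), or one final dose (after Week 82 through 88).
- TEAE tail: 105 days = 15 weeks (SAP 11.2.1).
- Planned numbers: Protocol 7.7 and SAP 4.3.

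**1. The plan's own figure.** The documents give no AE rate or patient-year total, so the sample size is used to size the withdrawn group. For 90% vs 75%, two-sided 0.05, 90% power and 1:2 allocation (pooled variance, no continuity correction), the active arm needs 102; power at 102:204 is 0.902. Then 102 × 3 / 0.8 = 382.5, rounded up to 383. Both match. With 400 in Arm 1, 400 × 0.8 = 320 responders: 107 continue, 213 are withdrawn. There are also 80 non-responders and 100 Arm 2 patients.

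**2. One withdrawn patient, retreated at Week R (dose = risankizumab dose)**
- R from 32 to 70: formula (R + 16) + 15 = R + 31; countable (16 + 15) + (16 + 15) = 62.
- After 70 through 82: formula R + 19; countable 31 + 19 = 50.
- After 82: formula R + 15; countable 31 + 15 = 46.
- The uncounted gap is R − 31 weeks throughout.

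| R | Formula, weeks | Countable, weeks | Rate too low by |
|---|---|---|---|
| 32 | 63 | 62 | 1.6% |
| 52 | 83 | 62 | 25.3% |
| 70 | 101 | 62 | 38.6% |
| 82 | 101 | 50 | 50.5% |

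**3. Pooled ALL_RZB rate.** Assumptions: no dropout, full follow-up, and no relapse among continued or Arm 2 responders. Continued patients and non-responders contribute 88 + 15 = 103 weeks each. Arm 2 contributes (88 − 16) + 15 = 87. A withdrawn patient never retreated contributes 31.

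Base without the withdrawn group = 187 × 103 + 100 × 87 = 27,961 patient-weeks.

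The withdrawn group adds 213 × the mean of the step 2 values (31 if never retreated). Relapse is taken at constant hazard from Week 28 to Week 88, and any relapse arising before Week 32 is placed at Week 32. If p relapse by Week 52, the share retreated by Week 88 is 1 − (1 − p)^(60/24): 12% for p = 5%, 51% for p = 25%.

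| Relapse by Week 52 | Countable | Formula | Rate too low by |
|---|---|---|---|
| 5% | 35,261 | 35,940 | 1.9% |
| 10% | 35,914 | 37,188 | 3.4% |
| 15% | 36,524 | 38,312 | 4.7% |
| 25% | 37,620 | 40,200 | 6.4% |
| 27.5% | 37,868 | 40,599 | 6.7% |

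The last row uses the largest loss of response in Protocol Table 7.7:1 as if it were relapse.

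Timing matters as much as frequency. With a fixed 25% retreated, countable time is 36,215. The formula gives 36,268 if all relapse at Week 32 (0.1% low), 37,333 at Week 52 (3.0%) and 38,292 at Week 70 (5.4%).

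**4. If placebo doses count as doses**, still against ALL_RZB events. A never-relapsing withdrawn patient has 88 + 15 = 103 formula weeks against 31 countable. The denominator is 49,430 at 5% relapse (28.7% low) and 47,670 at 25% (21.1% low). Counting Arm 2 from Week 0 adds 100 × 16 = 1,600 weeks: 51,030 (30.9%) and 49,270 (23.6%).

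**5. Would the SAP 9.0 exposure do instead?** Its 84-day tails give 28 + 28 = 56 weeks for a patient relapsing by Week 70, against a 62-week event window: 62/56 = 1.107, so that patient's rate is 10.7% too high. Pooled, 35,261/33,684 = 1.047 (5% relapse) and 37,620/35,792 = 1.051 (25% relapse).

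**The case against.** The strongest reply is that the premise is not in the text: the rate section never mentions ALL_RZB. Its wording is close to the general TEAE rule in 11.2.1 and to the entire-study final observation in SAP 6.0, both tied to study drug and 105 days. Read that way, numerator and denominator windows agree and there is no bias. The table list that would settle the matter is not available. This stands as a limit, which is why the point is conditional. But SAP 5.1 defines no whole-study, all-study-drug safety population to which that reading could apply.

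It can also be said that a programmer would meet the gap rule in 9.0, 11.3, 11.4 and the TEAE definition, and would apply it. The rate section, however, gives its own explicit formula with a different tail from 9.0, so 9.0 cannot simply be read into it.

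The 21% to 31% figures mix a study-drug denominator with a risankizumab numerator, and a consistent study-drug reading would have no mismatch. They are therefore a secondary case, though one the literal wording permits.

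The main range rests on assumptions. The documents give no rate of relapse (sPGA of 3 or more), and the 25% in Protocol 7.7 is loss of sPGA 0 or 1, a weaker event. Allowing up to 10% relapse among continued and Arm 2 responders moves 6.4% only to about 6.6%.

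Finally, the rate is descriptive, and Protocol 7.3.4 plans no safety hypothesis test. That limits the weight of the point but does not remove it.

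**Conclusion.** The concern holds, on the condition that the rate is produced for ALL_RZB. The stated denominator then contradicts that population's event rule, and the error always lowers the rate.

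With dose read as risankizumab dose, the pooled rate is 1.9% to 6.4% too low for 5% to 25% relapse by Week 52, under the constant-hazard and complete-follow-up assumptions above. It approaches zero if relapses cluster near Week 32. If placebo doses are counted, the shortfall is 21% to 31%. The direction is certain as soon as any withdrawn patient is retreated more than 105 days after the Week 16 dose; the size is not, because relapse frequency and timing are not in the documents.

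AE counts, percentages and the Safety_A1 and Safety_B_R comparisons are untouched. It should be corrected before the table is programmed, but it does not threaten the trial's main conclusions.

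**What to change.** In the patient-years paragraph of SAP 11.2.1:
- Name ALL_RZB as the population and state that dose means risankizumab dose.
- Define patient-years as the sum of risankizumab segments. For patients re-randomised to placebo, take Part A and retreatment separately, as 9.0 does, but with a 105-day tail in place of 84 so that it matches the TEAE window. Each segment ends no later than the start of the next.
- Do not reuse the 84-day tails unchanged, since that overstates the rate.

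Separately, and only if the rate is produced at the Week 52 analysis, cap both exposure and events at the data cut-off, as 9.0 already does for exposure. A last dose 0 to 84 days before the cut-off otherwise leaves 105 to 21 days of exposure beyond it.

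The cost is a few lines of text and one revised derivation. Reported AE rates become slightly higher.

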11.2.2 SAEs (Including Deaths) and Adverse Events Leading to Study Drug Discontinuation

Deaths and all SAEs will be presented in listing format. In addition, SAEs and AE leading to study drug discontinuation will be summarized by System Organ Class and MedDRA Preferred Term.

11.2.3 Safety Subgroup Analysis

The AE overview and AE by SOC and PT in Safety_A1 and Safety_B_R populations will also be analyzed with respect to the actual values of stratification factors:

- Dichotomous weight (≤ 100 kg vs. > 100 kg)
- Prior exposure to TNF antagonists (0 versus ≥ 1)

11.3 Analysis of Laboratory Data

For the assessments of laboratory data, values observed more than 105 days after the last dose of study drug will be excluded.

Listing and descriptive statistics of laboratory values over time, changes from baseline, and extreme abnormal value on treatment will be provided. Extreme abnormal value is the value which is most significantly away from the reference range. Frequency of subjects with transitions relative to reference range and listing of subjects with significant abnormal laboratory values will be presented as well.

Analyses will be conducted in the Safety_A1 Population, the Safety_B_R Population, and the ALL_RZB Population.

For subjects who were re-randomized to placebo in Part B, laboratory values evaluated after 105 days from the last dose of risankizumab in Part A and before the first dose of retreatment will not be included in the summaries for the ALL_RZB Population.

